**Electrical stimulation effect on coronally advanced flap
for the treatment of single gingival recession:
randomized controlled clinical trial**

UNESP – São Paulo State University. Dept. of Periodontology, College of
Dentistry

ClinicalTrial.org- NCT02987231

São José dos Campos, São Paulo - Brazil

August 15th, 2016

STUDY PROTOCOL

This investigation was a parallel, double-blind, randomized clinical trial. The study protocol (ClinicalTrial.org- NCT02987231) was approved by the Institutional Review Board at College of Dentistry – São José dos Campos, State University of São Paulo (1.679.369-UNESP). Each subject provided informed consent after a thorough explanation of the nature, risks, and benefits of the clinical investigation.

Study Population

Sixty patients from the Periodontology Clinic, UNESP—State University of São Paulo (São José dos Campos, Brazil), presenting 60 maxillary buccal gingival recessions in their canines and premolars were included in the study. The subjects were selected in the period between October 2016 and December 2017, according to the following eligibility criteria: 1) ≥ 18 years 2) periodontally and systemically healthy 3) FMPS and FMBS $\leq 20\%$ 4) single Cairo's class RT1 gingival recession (Cairo et al., 2011) in the maxillary canines or premolars ($\geq 3\text{mm}$ depth) at the buccal 5) presence of identifiable CEJ 6) no previous periodontal surgery at the affected teeth. Study exclusion criteria: 1) systemic problems that would contraindicate the surgical procedure; 2) patients taking medications known to interfere with the wound healing process or that contraindicate the surgical procedure; 3) smokers and pregnant women; 4) patients who underwent periodontal surgery in the area of interest; 5) patients undergoing orthodontic treatment.

Before surgery, Patients received oral hygiene instructions (roll technique) with a soft-bristled toothbrush to correct wrong habits related to the etiology of the recession. All participants received a session of prophylaxis and scaling. The surgical treatment was performed only when patients achieved adequate plaque control (full-mouth plaque score $\leq 15\%$)

Sample size

The sample dimension was calculated using $\alpha = 0.05$ and the power of 80%. For the standard deviation (SD), the value of 0.8 mm obtained in a previous paper (Jepsen et al. 2013). Thus, study was powered to detect a minimum clinically significant difference in root coverage of 0.8 mm between the test and control treatments for root coverage after 6 months. On the basis of these data, the minimum needed number of

patients to be enrolled in this study resulted 28 for the test group (CAF) and 28 for the control group (CAF+ES).

Randomization, allocation concealment, and blinding

The randomization process was performed by an external person who did not participate in the study. Patients were assigned to one of the two treatment groups with the use of computer-generated randomization sequence. Allocation concealment was obtained using sealed coded opaque envelope containing the treatment to the specific subject. The sealed envelope containing the treatment assignment was opened immediately after the surgical procedure by the investigator responsible for the electrical stimulation protocol. The surgeon, patients and investigators who performed clinical measurements were blinded to procedures.

Surgical procedure

All surgical procedures were performed by a single operator ([name]). With a blade 15c (Surgi Blade® - Miami, FL - USA) two horizontal incisions were made at the bases of the mesial and distal papillae of the tooth, towards the adjacent teeth, taking care not to touch the adjacent teeth. From the end of the incisions, two divergent relaxing incisions were performed vertically in the apical direction that surpassed the mucogingival line so that the flap had mobility for coronary traction. A sulcular incision was performed in order to unite the releasing incisions and a split-full-split thickness flap was raised beyond the mucogingival junction (MGJ) (de Sanctis & Zucchelli 2007). After the root planing procedures were performed, the epithelial layer was removed from the incised papillae exposing the connective tissue. Before the flap was positioned coronally, the region was washed copiously with physiological solution to remove the clot allowing intimate contact of the flap with the recipient bed. Sling sutures (5.0 Vicryl™; Ethicon Inc, São José dos Campos, Brazil) were placed to stabilize the flap 2 mm coronal to CEJ, followed by interrupted sutures to close the releasing incisions.

Electric Stimulation Protocol

The patients allocated in the CAF+ES group received the protocol for electrical stimulation. A unit consisting of a signal generator (Keysight Technologies., Inc., Santa Rosa-CA, USA), a power supply and circuit board, was assembled. Conductive electrodes for electrical current application were positioned on each side of the flap, at a

mean distance of 3 mm from the relaxing incisions and an alternating current with intensity of 100 μ A at 9 kHz, was distributed in order to traverse the operated region. Patients received the stimulus applications for 120 seconds, once a day for 5 consecutive days. The electrical current was optimized through an oscilloscope (Keysight Technologies., Inc., Santa Rosa-CA, USA). All applications were performed by a single researcher involved in the study ([name]). Patients randomized to the CAF group received the simulation of the electrical stimulation process.

Clinical Assessments

Clinical parameters were evaluated at baseline, 3 and 6 months postoperatively as follows: 1) full-mouth visible plaque index (FMPI) (Ainamo & Bay 1975), and presence or absence of visible plaque accumulation at the site included in the study (plaque index [PI]); 2) full-mouth sulcus bleeding index (FMBI) (Muhlemann & Son 1971), and presence or absence of bleeding on probing (BOP) at the site included in the study; 3) PD: measured in millimeters with a periodontal probe (XP23/UNC-15, Hu-Friedy, Chicago, IL); 4) relative GR (RGR): distance from the gingival margin to the incisal border of the tooth; 5) RCAL: measured as PD+RGR; 6) GR: measured at the mid-buccal aspect of the tooth (both RGR and GR quantified using a caliper with a precision of 0.01mm and a pair of dividers); 7) keratinized tissue width (KTW); and 8) keratinized tissue thickness (KTT): measured at the midpoint location between the gingival margin and mucogingival junction as previously described (Fernandes-Dias et al., 2015). A masked and calibrated investigator ([name]) carried out all clinical evaluations. The examiner calibration was performed for PD and RGR using Kappa statistic and intra-class correlation ($k = 0.88$ and $ICC = 0.81$, respectively).

Esthetic evaluation

To assess the final aesthetic outcome, two analyses were performed, one professional e one patient-centered. The professional evaluation was assessed using the Root Coverage Esthetic Score (RES) (Cairo et al. 2009). For this, two examiners performed the evaluations ([name] and [name]) 6 months after surgeries. The examiners presented previous experience in cosmetic dentistry, were blinded for the treatments and were previously calibrated (intra and inter-examiners $K>0.8$). Esthetic outcomes were also evaluated from the patient's point of view, using a VAS scale pre- and 6 post-operative.

Patient-centered outcomes

At the end of the first postoperative week, the patients completed a questionnaire about the occurrence of discomfort and postoperative pain. The pain was rated by the patient on a VAS scale of 0 to 10 (0 = no sensitivity and 10 = extreme pain). In addition, the patients were asked to report the number of analgesic pills they consumed that week. Dentin hypersensitivity was assessed by 5 s air blast from a triple syringe, applied to the exposed buccal cervical area. A visual analogue scale (VAS) scale (0 = no pain, 10 = extreme pain) was used to record DH related to stimulus. DH was recorded at baseline, 3 and 6 months postoperatively.

Sampling and immunological evaluation

The samples were collected as previously described (Santamaria et al., 2013). Briefly, gingival crevicular fluid (GCF) was collected from the vestibular region of the site that received the CAF. Sampling was performed by introducing filter paper strips (Periopaper; Proflow Inc., Amityville, NY, USA) into sulci until mild resistance was felt, removed after 20 s, and collected fluid volume immediately determined by calibrated instrument (Periotron 8000; Ora Flow Inc., Plain View, NY, USA). The strips were placed in sterile tubes containing 300 ml of phosphate buffered saline (PBS) with 0.05% Tween-2. Strips contaminated with visible blood were discarded. All GCF samples were stored immediately at -80° C. Samples were collected at baseline (before surgery), and 7, 14, 30, 60 and 90 days after surgery.

Levels of Cito / chemokines were determined by a multiplex immunoassay. Aliquots of each GCF sample were tested using a commercial human kit (Millipore Corporation, Billerica, MA, USA), in order to evaluate levels of the following inflammatory markers: interleukin (IL)-1 β , IL-6, IL-10, tumoral necrosis factor α (TNF α), macrophage inflammatory protein-1 α (MIP-1 α), and chemotactic protein for monocytes-1 α (MCP-1 α). In addition, matrix metalloproteinases (MMP)-2, MMP-9, tissue inhibitor of metalloproteinases (TIMP)-1, TIMP-2 and VEGF were also evaluated. Sample concentrations (antigens in gingival crevicular fluid samples) were estimated from the standard curve using standard kit proteins following manufacturer's instructions and expressed as pg / mL.

STATISTICAL ANALYSIS PLAN

Descriptive statistics were performed using mean \pm standard deviation (SD), and normality was tested using Shapiro-Wilk tests. The PD, RGR, CAL, KTT, KTW, and DH values and also inflammatory markers / growth factors were examined by two-way repeated measures ANOVA to evaluate the differences within and between groups, followed by a Tukey test for multiple comparisons when the Shapiro-Wilk p value was ≥ 0.05 . Data presenting Shapiro-Wilk p values < 0.05 were analyzed using Mann-Whitney tests (for intergroup comparisons) and a Friedman test (for intragroup comparisons). Postoperative discomfort, patient's esthetics measured through VAS and intergroup RES comparisons were analyzed by T-tests. The frequency of complete root coverage (CRC) was compared using χ^2 tests. For all tests a significance level of 0.05 was adopted.

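### The printed sample-size inputs give 16 to 17 patients per group, not the stated minimum of 28, so an input, an unstated adjustment or the number itself is misreported

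*Combined protocol and SAP*

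**What the plan says.** All the inputs are in the Sample size section of the protocol:

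- Error rates: "The sample dimension was calculated using $\alpha = 0.05$ and the power of 80" per cent.
- Variability: "For the standard deviation (SD), the value of 0.8 mm obtained in a previous paper".
- Target: "Thus, study was powered to detect a minimum clinically significant difference in root coverage of 0.8 mm between the test and control treatments", with 6 months as the time point.
- Result: "On the basis of these data, the minimum needed number of", continuing after a page break with "patients to be enrolled in this study resulted 28 for the test group (CAF) and 28 for the control group (CAF+ES".

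The section names no test, does not say whether the test is one- or two-sided, and mentions no allowance for dropout, multiplicity or non-normal data. The Statistical Analysis Plan adds only "For all tests a significance level of 0.05 was adopted". The Study Population section describes a larger number than the minimum, with sixty patients "presenting 60 maxillary buccal gingival recessions in their canines and premolars were included in the study".

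**The concern.** The section presents 28 per group as the consequence of the inputs listed just before it. With the difference equal to the SD, the standardised effect is exactly 1.0, and a trial looking for an effect of one SD at 80% power needs far fewer than 28 per group. At least one element of the paragraph must therefore be misreported, or an adjustment was made and not described.

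This paragraph is the plan's only statement of the difference the trial was designed to detect. If it does not hold together, a reader facing a null or borderline 6-month result cannot tell whether the trial had about 96% power for 0.8 mm or only 80%.

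**Working it through.** **Inputs (Sample size section):** alpha 0.05; power 0.80; SD σ = 0.8 mm; difference δ = 0.8 mm; equal groups. **Assumed:** two-sided test, comparison of two independent means (the trial is described as parallel).

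**Attempt to reproduce 28**

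Normal formula: n per group = 2 (z₀.₉₇₅ + z₀.₈₀)² σ² / δ²

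= 2 × (1.960 + 0.842)² × 0.8² / 0.8² = 2 × 7.849 × 1 = 15.70, so 16.

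The t-test (noncentral t, standardised effect 1.0) gives 16.71, so 17.

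Gap: 28 − 17 = 11 per group, and 11/17 = 65%. The stated figure is not reproduced.

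**Variants that keep the four stated inputs**

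| Variant | n per group |
|---|---|
| One-sided t-test | 13.10, so 14 |
| Rank test, efficiency 0.955 | 16.71 / 0.955 = 17.5, so 18 |
| Rank test, efficiency 0.864 | 16.71 / 0.864 = 19.3, so 20 |

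None reaches 28. Two one-sided groups of 14 total 28, but the text gives 28 for each group.

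**What would have to change to reach about 28, one item at a time**

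| Item | Value needed | Check |
|---|---|---|
| Difference | about 0.6 mm | 15.70 × (0.8/0.6)² = 27.9; t-test 28.9 |
| SD | about 1.05 mm | 15.70 × (1.05/0.8)² = 27.0; t-test 28.0 |
| Power | about 96% | t-test power at 28 per group is 95.7% |
| Dropout allowance | about 39% | 1 − 17/28 = 0.39 |
| Alpha | about 0.006 | t-test, 0.0057 |

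At 95% power the t-test needs 26.99, so 27: close to 28, but contrary to the stated 80%. These values are solved backwards from 28. They show how large a slip is needed, and are not evidence of which slip occurred.

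**What 28 per group delivers (t-test, two-sided 0.05)**

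Power for a difference of 0.8 mm, by true SD; the 30-per-group column applies only if the 60 patients were split equally:

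| SD (mm) | 28 per group | 30 per group |
|---|---|---|
| 0.8 | 95.7% | 96.8% |
| 0.9 | 90.4% | 92.3% |
| 1.0 | 83.6% | 86.1% |
| 1.05 | 80.0% | 82.7% |
| 1.1 | 76.2% | 79.1% |

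With SD 0.8 mm, the difference detectable at 80% power is 0.61 mm at 28 per group and 0.59 mm at 30.

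**The case against.** The best defence is that nothing is lost. On the printed inputs the trial has more patients than it needs, sixty were included against a minimum of 56, and power for 0.8 mm stays at about 80% or better for any SD up to roughly 1.05 mm at 28 per group. The plan also does say which difference it targets. This stands as far as it goes: the discrepancy does not show an underpowered trial, and the harm lies in reproducibility and in the exact power and detectable difference. It does not make the paragraph correct, because the reassurance depends on the printed SD and difference being the right ones, and the mismatch puts exactly that in doubt.

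A second point is that no test is named. The Statistical Analysis Plan uses repeated-measures ANOVA or rank tests for its clinical measures, and it is not said whether the SD refers to a single visit or to a change. So 16 to 17 is conditional on a two-group comparison of means. That is a fair qualification, but it does not recover 28. The rank-test allowance stops at 20. Reading 0.8 mm as a single-visit SD, with uncorrelated visits, gives an SD of change of 0.8 × √2 = 1.13 mm and 32 to 33 per group.

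A third is that an inflation may simply have been left out. It may, but it would have to be about 39% if it were for dropout, and the text calls 28 the minimum needed. An omitted adjustment calls for the same correction.

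**Conclusion.** The concern holds. For a two-sided comparison of two independent means, the stated inputs give 16 (normal) or 17 (t-test) per group against the stated 28, and no variant tried that keeps those inputs and adds nothing unstated closes the gap. The conclusion rests on the assumed test and sidedness; a one-sided test widens the gap. Which item is wrong cannot be settled from the documents.

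If the printed SD and difference are right, the error is conservative: power at 28 per group is about 96%, not 80%. If the SD is the misprinted item, at about 1.05 mm, the stated 80% is right. This should be fixed as a matter of reporting; it does not call the adequacy of enrolment into question.

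**What to change.** Rewrite the sample-size paragraph from the original calculation record. State the test, sidedness, difference, SD (and whether it is for a single visit or a change), power and any inflation, so that the inputs yield the number given.

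If the record confirms 0.8 mm for both difference and SD, say that 16 to 17 per group were needed for 80% power and that 28 per group gives about 96% power for 0.8 mm, with about 0.61 mm detectable at 80% power. For 30 per group, if the split was equal, the corresponding figures are about 97% and 0.59 mm. Do not replace the 0.8 mm threshold with a value fitted back to the sample size.

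In the same edit, reconcile the group labels. The Sample size section calls CAF the test group and CAF+ES the control, whereas the Electric Stimulation Protocol section has "Patients randomized to the CAF group received the simulation of the electrical stimulation process". This is clerical and does not affect the arithmetic.

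The cost is one corrected paragraph, with no extra patients and no change to the analysis.

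### The trial is sized on 0.8 mm of root coverage, but the SAP analyses no root coverage in mm, and its only mm recession variable (RGR) has no limit at the CEJ

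*Combined protocol and SAP*

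**What the plan says.** The Sample size section sets the target as a "minimum clinically significant difference in root coverage of 0.8 mm between the test and control treatments for root coverage after 6 months". It takes 0.8 mm as the SD and arrives at 28 patients per group. It does not say how root coverage is computed.

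The Clinical Assessments section defines "relative GR (RGR): distance from the gingival margin to the incisal border of the tooth". GR is listed there as a separate item, read at the mid-buccal point at baseline, 3 and 6 months. Neither its reference point nor the handling of a margin coronal to the CEJ is stated.

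The Surgical procedure section says that the sutures "were placed to stabilize the flap 2 mm coronal to CEJ". The allocation envelope is opened only after surgery, so this position is common to both arms.

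The Statistical Analysis Plan puts PD, RGR, CAL, KTT, KTW, DH and the markers through repeated measures ANOVA, or Mann-Whitney and Friedman tests if Shapiro-Wilk fails. Neither GR nor root coverage in mm appears. Complete root coverage (CRC) is compared by chi-square and is not defined.

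**The concern.** Root coverage ends at the CEJ, because beyond it there is no root left to cover. RGR does not end there: a millimetre of gingiva kept over enamel lowers it exactly as a millimetre of newly covered root does. RCAL, defined as PD plus RGR, has the same property. Since the flap is placed beyond the CEJ on purpose, healing over enamel is foreseeable.

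Followed as written, the SAP therefore tests margin movement, while the trial was sized on root coverage. Adjusting for baseline does not help, because a baseline-adjusted change in RGR is still margin movement. At stake is whether the 0.8 mm target can be declared met or missed on the quantity for which it was set.

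**Working it through.** **The plan's own figure.** With two-sided alpha 0.05 (sidedness is not stated), 80% power, SD 0.8 mm and difference 0.8 mm, n per group = 2 × (1.960 + 0.842)² × (0.8/0.8)² = 15.7, so 16, or 17 with the t distribution. The stated 28 does not reproduce. At 28 per group the power for 0.8 mm is about 96%. That calculation needs explaining, but it is a separate matter and is not a shortage of power on the stated inputs.

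**Inputs.** The 0.8 mm difference, SD 0.8 mm and 28 per group come from the Sample size section. The 6-month margin position is in neither the protocol nor the SAP. I assume it is normal with equal SD in both arms, use SD 0.8 mm as the main case, and vary the control mean.

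**Formulas.** Let r be the 6-month margin position, positive when apical to the CEJ. RGR equals r plus the distance from CEJ to incisal border, which is fixed for a tooth. With balanced or adjusted baselines, the arm difference in RGR is therefore the difference in mean r. Residual recession is max(r, 0), and for r normal with mean m and SD s:

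E[max(r, 0)] = m·Φ(m/s) + s·φ(m/s)

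The root-coverage difference is this value at m (control) minus its value at m − 0.8 (stimulated). The RGR difference is 0.8 mm in every row below.

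| Control mean, mm apical to CEJ | Control residual (mm) | Stimulated residual (mm) | Root-coverage difference (mm) |
|---|---|---|---|
| 0.72 | 0.80 | 0.28 | 0.52 |
| 1.0 | 1.04 | 0.43 | 0.61 |
| 1.6 | 1.61 | 0.87 | 0.74 |
| 2.0 | 2.00 | 1.22 | 0.78 |

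First row in full: 0.72 × Φ(0.9) + 0.8 × φ(0.9) = 0.72 × 0.816 + 0.8 × 0.266 = 0.80. For the stimulated arm, −0.08 × Φ(−0.1) + 0.8 × φ(−0.1) = −0.037 + 0.318 = 0.28. The difference is 0.52.

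**Why the table starts at 0.72.** A planned gain of 0.8 mm in root coverage needs at least 0.8 mm of exposed root in controls on average. With SD 0.8 mm that requires a control mean of about 0.72 mm apical.

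**Sensitivity to the SD.** At control means of 1.0, 1.5 and 2.0 mm, the root-coverage difference is 0.69, 0.78 and 0.80 mm with SD 0.5, and 0.58, 0.69 and 0.75 mm with SD 1.0.

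**Unequal spreads.** Control mean 0.4 with SD 0.9 against stimulated mean 0.2 with SD 0.3 gives an RGR difference of 0.20 mm, but a root-coverage difference of 0.594 − 0.245 = 0.349 mm. RGR understates here.

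**No difference in margins.** If the two arms have the same distribution of r, both measures give zero.

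**The case against.** A reader might infer that the plan reports gingiva over enamel as root coverage and so inflates the treatment effect. The documents do not support that reading, for four reasons.

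- No section says that RGR change will be called root coverage. The SAP lists RGR under its own name.
- The 2 mm is the position at suturing, not at 6 months, and it is the same in both arms. Identical healing gives no false difference.
- CRC is in substance a CEJ outcome. If stimulation only preserved gingiva over roots already covered, CRC would show no gain.
- The most alarming cases conflict with the trial's premise. With SD 0.8 mm, control means at the CEJ and 0.4 mm apical give root-coverage differences of 0.25 and 0.40 mm. But they leave controls only 0.32 and 0.56 mm of exposed root, so a 0.8 mm gain could not occur.

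All four points stand, and they limit the claim. They do not remove it. If RGR is not meant to test the 0.8 mm target, then nothing in mm does. Identical margins are also not the same as equal root coverage. If every root were covered, with control margins 0.2 mm and stimulated margins 1.0 mm coronal to the CEJ, RGR would differ by 0.8 mm and root coverage by zero. This shows that the two quantities differ; it is not a forecast. CRC, being yes/no and undefined, cannot say whether 0.8 mm was reached.

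**Conclusion.** The gap between the sizing variable and the analysed variables can be read directly from the documents. Its numerical effect is conditional. With normal margin positions, equal SDs of 0.8 mm and a 0.8 mm RGR difference, RGR exceeds the root-coverage difference by about 0.28 mm (0.80 − 0.52) when control margins average about 0.7 mm apical to the CEJ. The excess is about 0.06 mm at 1.6 mm apical and negligible from 2 mm on. Overstatement is the usual direction under equal spreads, but it is not established, and unequal spreads can reverse it. A threefold overstatement (0.8/0.25) is tempting to quote, but it needs control margins centred on the CEJ, which nothing in the documents supports and which the sizing premise rules out in this model. The point should be corrected in the SAP; it does not invalidate the trial.

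**What to change.** In the SAP:

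1. State that GR is measured from the CEJ. Define root coverage per patient as baseline GR minus 6-month GR, with GR set to 0 when the margin is at or coronal to the CEJ.
2. Make the between-group comparison of this variable at 6 months the analysis of the 0.8 mm target.
3. Keep RGR as a secondary outcome labelled as margin position.
4. Report by arm how many margins healed coronal to the CEJ, and define CRC by the same rule.

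Use GR directly. The smaller of baseline GR and RGR change equals the floored GR change only if nothing is measured with error, and taking the minimum of noisy readings biases coverage downward. Examiner calibration is reported for PD and RGR but not for GR, which should be acknowledged.

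The cost is SAP wording and one derived variable, since GR is already scheduled at baseline and 6 months. The capped outcome has a ceiling, so the difference may be smaller, and it may fail Shapiro-Wilk and go to Mann-Whitney. In the model with SD 0.8 mm and a 0.8 mm margin shift, t-test power at 28 per group is about 94% with the control mean 1.0 mm apical and 96% at 1.5 mm, against 96% for RGR. Capping therefore costs little power there.

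### Dentin hypersensitivity is compared in all patients with no baseline adjustment, so any teeth scoring 0 at entry weaken the comparison between arms

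*Combined protocol and SAP*

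**What the plan says.** **Entry criteria (Study Population).** The six inclusion and five exclusion criteria cover age, general and periodontal health, plaque and bleeding scores, recession type, depth and site, "presence of identifiable CEJ", earlier surgery, medication, smoking, pregnancy and orthodontic treatment. None concerns sensitivity, so a non-sensitive tooth with a recession of 3 mm or more is eligible.

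**Measurement (Patient-centered outcomes).** DH is the response to an air blast, scored 0 to 10 with 0 as no pain. "DH was recorded at baseline, 3 and 6 months postoperatively".

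**Analysis (Statistical Analysis Plan).** "The PD, RGR, CAL, KTT, KTW, and DH values and also inflammatory markers / growth factors were examined by two-way repeated measures ANOVA" when Shapiro-Wilk gives p of 0.05 or more. Otherwise the plan uses "Mann-Whitney tests (for intergroup comparisons") and a Friedman test within groups. No baseline covariate and no baseline-DH subset is named for either branch.

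**Sample size.** The calculation concerns root coverage: "minimum clinically significant difference in root coverage of 0.8 mm between the test and control treatments". No effect, SD or power is given for DH.

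**The concern.** The DH scale has a floor at 0. A tooth that starts there cannot show relief in either arm. Such teeth add tied zeros to both arms and pull the two means together. Neither named test uses the baseline score to separate these teeth from those with sensitivity to lose.

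A real effect on sensitivity could then be reported as no difference. The mean difference would also average over teeth with nothing to relieve, and so understate the effect in sensitive teeth.

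**Working it through.** **1. The plan's own figure.** The only one is 28 per group, for root coverage. With a difference of 0.8 mm, SD 0.8 mm, two-sided alpha 0.05 and 80% power, the normal formula gives 2 × (1.960 + 0.842)² × (0.8/0.8)² = 15.7, so 16 per group. The stated 28 is not reproduced. That is a separate matter, because neither number says anything about DH.

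**2. Closed-form check.** From the documents: 60 patients, alpha 0.05. Assumed: 30 per arm; two-sided test; a share p of teeth sensitive at entry; the rest at 0 throughout. Let d be the standardised effect among sensitive teeth, and r the mean of the analysed DH value among sensitive teeth divided by its SD. In units of that SD:

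- difference between arms = p × d
- SD = √(p + p(1 − p)r²)
- power = Φ( (difference / SD) × √(30/2) − 1.960 )

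Set d so that power is 80% when every tooth is sensitive: d = (1.960 + 0.842)/√15 = 0.723.

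For p = 0.7 and r = 1, the difference is 0.7 × 0.723 = 0.506 and the SD is √(0.7 + 0.21) = 0.954. Power is Φ(0.531 × 3.873 − 1.960) = Φ(0.096) = 54%. Sensitive teeth alone (21 per arm) give Φ(0.723 × √10.5 − 1.960) = 65%.

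| Share sensitive | All, r = 0.5 | All, r = 1 | All, r = 2 | Sensitive only |
|---|---|---|---|---|
| 100% | 80% | 80% | 80% | 80% |
| 90% | 75% | 72% | 61% | 76% |
| 80% | 69% | 63% | 46% | 71% |
| 70% | 62% | 54% | 35% | 65% |
| 50% | 46% | 37% | 21% | 51% |

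Part of the loss is simply fewer informative teeth, which a subset analysis does not recover.

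**3. Simulation, first scenario (all DH inputs assumed).** 30 per arm. Sensitive teeth have baseline mean 5, SD 2. The 6-month latent mean is 2.4 against 1.2, SD 1.8, correlation with baseline 0.4, cut off at 0. Other teeth stay at 0. Power at 6 months:

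| Share at 0 | Mann-Whitney, all | Mann-Whitney, DH > 0 | Change-score t-test, all | Baseline-adjusted model, all |
|---|---|---|---|---|
| 0% | 68% | 68% | 49% | not tabulated |
| 10% | 55% | 65% | not tabulated | 73% |
| 20% | 40% | 59% | 30% | 65% |
| 40% | 22% | 46% | 19% | 51–54% |
| 60% | 12% | 31% | 13% | 35% |

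Repeat runs differ by two or three points. The Mann-Whitney loss is 68 − 55 = 13, 68 − 40 = 28 and 68 − 22 = 46 points at 10%, 20% and 40%. The mean difference is about 1.0 × (1 − share at 0), so 0.8, 0.6 and 0.4 points at 20%, 40% and 60%.

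With two visits, the group-by-time test of a repeated measures ANOVA is the change-score t-test. The planned three-visit version was not simulated.

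**4. Which branch applies.** In the same scenario, Shapiro-Wilk rejected normality in at least one arm in 93% of runs with none at 0, and in over 99% with 20% at 0. Mann-Whitney is therefore the likely branch, mainly because of the floor itself.

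**5. Second scenario.** Baseline mean 5, control mean 3 after treatment, SD 2, effect 1.5, correlation 0.5. Going from 100% to 70% sensitive, Mann-Whitney falls from 79% to 36% (subset 62%), the change-score t-test from 73% to 41% (subset 59%), and the adjusted model from 89% to 76% (subset 76%).

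**The case against.** **The size is unknown.** This stands. The documents give no share at 0, no DH effect and no DH SD. Every enrolled tooth has at least 3 mm of recession and the air is directed at the exposed area, so an exact 0 may be uncommon. A reader might infer that the trial loses much of its DH power. That follows only if a substantial share start at 0. In the closed form with r = 1, the loss is about 8 points at 90% sensitive and 43 points at 50%.

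**No planned DH power exists to lose.** This also stands. The trial was sized on root coverage, and in the first scenario Mann-Whitney reaches only about 68% even with every tooth sensitive. DH is still a planned comparison at the 0.05 level, so its efficiency matters.

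**The all-patient comparison is valid.** Correct. Randomisation makes it unbiased for the enrolled population. A reader might infer bias, or that the trial cannot answer its DH question. Neither follows: it estimates an average effect over a population that may include non-sensitive teeth.

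**Teeth at 0 may become sensitive after surgery.** Possible, and the calculations hold them at 0. When 10% of them were allowed to become sensitive, power barely moved (23% against 45% for the restricted test, with 40% at 0). They should still stay in the main analysis.

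**Being sent to Mann-Whitney is not itself the harm.** Agreed. Among all patients it has more power than the change-score test at 20% and 40% at 0. The gap is that neither named method conditions on baseline DH.

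**Conclusion.** The concern holds in conditional form. Eligibility does not require sensitivity, the scale has a floor, and the SAP neither adjusts for baseline DH nor plans a comparison in teeth sensitive at entry. If some teeth start at 0, the difference between arms shrinks and the named tests lose power. In the first scenario the Mann-Whitney loss runs from none, with no teeth at 0, to 46 points with 40% at 0.

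These sizes rest on assumed DH means, SDs, correlations and effects, 30 per arm, and teeth at 0 staying at 0. The direction under those assumptions does not depend on the exact values; the amount does.

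A reader might also infer that the entry criteria are wrong. The documents do not support that. Root coverage is the sizing outcome, and the weakness can be handled in the analysis. In the first scenario, adjustment in all patients gave more power than restricting Mann-Whitney to sensitive teeth at every share compared. This is a worthwhile improvement to an outcome on which the trial was not sized.

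**What to change.** In the SAP:

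1. Compare DH at 3 and 6 months between arms in all randomised patients, adjusted for baseline DH (for example ANCOVA), with a rank-based or bootstrap check for non-normality.
2. Pre-specify a supporting comparison, by assigned arm, in patients with baseline DH above 0. Adjustment regains precision, but the adjusted estimate still averages over teeth at 0; this comparison shows the effect in sensitive teeth. Baseline DH is a pre-surgery measure and the envelope is opened only after surgery, so selecting on it preserves the randomised comparison.
3. Report per arm the number with baseline DH of 0, and how many of those score above 0 at 3 and at 6 months.

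The cost is a few SAP sentences, slightly more analysis and an extra table row or two. The supporting comparison has fewer patients and applies only to teeth sensitive at entry. No new data and no change to eligibility are needed.
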